### 2.3.7 Efficacy of Romidepsin

Positive results were reported in 71 patients with CTCL treated on the multicenter NCI study of romidepsin administered as a 4-hour infusion on days 1, 8, and 15 of a 28-day cycle with a starting dose of 14 mg/m^2[19]. The ORR was 34%, with a CR observed in four patients, a PR in 20, and SD in 26. The median time to progression for patients with a major response (CR or PR) was 15.1 months.

Very encouraging responses have also been reported in patients with peripheral T-cell lymphoma (PTCL). ORR of 31%, as a single agent in 48 patients, including four CR and 11 PR [25]. The overall median duration of response for all patients was 9 months.

[figure not shown]
In 2011, the US FDA approved romidepsin for patients with relapsed/refractory PTCL.

## 2.4 Rationale for the Study

### 2.4.1 Hypothesis and Preliminary Data

Targeting HDAC's in patients with TCL has proven to be a valuable therapeutic approach [7]. Vorinostat became the first HDACi approved for the treatment of cancer, for patients with relapsed and refractory CTCL in 2006, followed in 2009 by the approval of romidepsin and expanded in 2011 to include patients with relapsed and refractory PTCL. The promising experience with HDACi in T-cell lymphoma, driven by empirical observations, established that targeting the 'epigenome' was a viable treatment strategy for select sub-types of lymphoma, albeit, effective in about one-third of all TCL patients [9]. Experiences from myeloid leukemia and myelodysplastic syndrome have suggested that combinations of epigenetically targeted drugs, including HDACi plus hypomethylating agents (HoMe), may have more therapeutic value than either of these agents alone. In addition, **HDACi shown to decrease DNMT-1**, leading to reduced genomic methylation and gene activation [15]. These data suggest that the overlapping influences HDACi and HoME on the epigenome could be exploited in rational combinations.

[figure not shown]
To date we have evaluated these two drug classes combination in a variety of preclinical models of cell lymphoma, [16], and have explored the influence of the individual drugs and their combination on gene expression in different sub-types of T-cell lymphoma. These data revealed substantial synergism between the hypomethylating agents (*decitabine and 5-azacitidine*) and various *HDACi including romidepsin, belinostat, vorinostat and panobinostat* with synergy coefficients ranging between 0.1 and 0.9 (see Figure below) [17]. While the synergy seen here was observed following a modest (~12 hr) lead in of the HoMe agent, it suggests a class effect between the different HDACi and the HoMe agent, where the IC10-20 of each drug against the specific cell line was used in the combination. These data also underscore the fact that there are many variables that determine

this degree of synergy, including the particular drug-drug combination, drug concentration, schedule and duration of exposure.

We recently showed that the combination of romidepsin and the HoMe agent decitabine reversed the malignant phenotype of all T-cell lymphoma cell lines tested, with each individual drug having only a partial effect on the expression signature (Figure 3) [17]. The GEP data also demonstrated that while common sub-sets of genes could be affected, the greatest number of ‘unique’ genes perturbed were seen in those cells treated with the combination, where nearly 1000 unique genes were altered, strongly supporting the hypothesis that the synergism seen at the cellular level and in the *in vivo* model, was also seen at the molecular level. The Venn diagram below illustrates the principle: the effects of the two drugs alone are largely different (only 39 genes modified in common by all the treatment groups), while most of the effects induced by the single agent treatment are maintained in the combination group (174 genes out of 191 for romidepsin and 211 genes out of 221 for decitabine). Interestingly, an additional 944 unique genes (i.e. genes not affected by the single agents) are modulated only by the combination treatment, strongly supporting the hypothesis of ‘molecular synergism’.

[figure not shown]
**Figure 1.** Cytotoxicity curves in H9 and HH following exposure to decitabine and HDAC inhibitor . The tables list synergy coefficients for the specified combination. [R=romidepsin;B=belinostat;S=SAHA; L=LBH589/panobinostat.] In subsequent experiments with a SCID Beige Xenograft Mouse Model of HH-CTCL, mice were treated i.p. for 3 cycles with decitabine, belinostat and the combination. Statistically significant tumor growth inhibition was observed in the combination cohort compared to all the others.

Collectively, these data suggest that dual targeting of the epigenome in T-cell lymphoma may represent an incremental improvement in our ability to treat the disease compared to single agent (or class) approaches predicated on HDAC inhibitors alone.

1. Of patients with Germinal Center (GC)-DLBCL treated with standard therapy, 30% will relapse (12) and less than half of these patients will be eligible for intensive salvage therapy (13). There is a need to improve therapeutic options as there are limited-to-no targeted approaches for salvaging patients with refractory GC-DLBCL. As we have reviewed in *Clinical Cancer Research* (14)(Fig 4), new discoveries into the molecular pathogenesis of this disease have created enthusiasm around the development of precision targeted strategies (Fig 5). Although it is known that mutations in BCL6, EZH2, histone acetyltransferases (HATs) and other epigenetic modifiers all contribute to silencing of tumor suppressors, it is not known what effects simultaneous epigenetic dysregulation have on the biology of GC-lymphomas, or their responsiveness to targeted treatment. *Given the clustering of epigenetic mutations in GC-derived lymphomas, the possibility of directly targeting HATs combined with targeting of complimentary epigenetic machinery may serve as a promising future treatment paradigm for this specific*

[figure not shown]
**Figure 4:** Schematic of derangements in Germinal Center Lymphoma

disease entity (**Fig 5**)(14). Past studies have focused on individually targeting these factors, but not studying them together as a whole. Our laboratory has made several pivotal observations regarding the targeting of epigenetic operations in DLBCL. Using a translational approach, we have taken direct observations from the laboratory and applied them to clinical trials. Some examples include: We have established that targeting the Bcl6 : p53 axis with HDAC and Sirtuin inhibitors inactivates Bcl6 and activates p53 leading to clinically meaningful responses in patients with lymphoma (Amengual Blood 2013)(8) (**Fig 6, 7**).

2. We have demonstrated that combinations of DNMT and HDAC inhibitors are synergistic in DLBCL and led to modulation of *SMAD1* and *DNMT3A* which are known to influence chemotherapy resistance (Kalac Blood 2011)(10) (**Fig 8**).

**Figure 5:** Schematic of epigenetic modulation in GC-lymphomas

[figure not shown]
**Modulating Acetylation of the Bcl6 : p53 Axis.** Small molecule inhibitors of HDACs help maintain transcriptionally active chromatin, theoretically allowing for expression of tumor suppressor genes (22). Three HDAC inhibitors, vorinostat (23, 24), belinostat (25), and romidepsin (26, 27), have been all approved by the FDA for the treatment of T-cell lymphoma. Despite approval in T-cell lymphoma, single agent HDAC inhibitors have demonstrated limited activity in relapsed DLBCL (28). *I have demonstrated that the combination of niacinamide (N), a sirtuin inhibitor, and HDAC inhibitors (romidepsin (R), vorinostat (V), belinostat (B), or panobinostat (P)) leads to synergistic cytotoxicity in GC-DLBCL but not ABC-DLBCL (Fig 6)*[Amengual, et. al (8)]. Figure 3 represents the synergy co-efficients of combinations of 4 different HDAC inhibitors with niacinamide in 8 DLBCL cell lines. Red boxes indicate synergistic interactions. As represented here, the GC-DLCBL cells are more sensitive to the combination. Our group developed a genetically engineered mouse (lambda-myc crossed with mCherry fluorescent CD19) which develops spontaneous B-cell lymphoma. This mouse model expresses similar levels of Bcl6 and p53 as the GC-DLCBL cell lines (29). Following exposure to romidepsin and niacinamide, mouse lymphoid tissue demonstrated acetylation of both Bcl6 and p53 measured by immunoprecipitation as well as modulation of downstream targets BLIMP1 and p21 measured by immunoblot (**Fig 7**). The combination was well tolerated in mice and led to increased tumor growth delay compared to either drug alone as measured by *in vivo* imaging (**Fig 7**). These findings demonstrated for the first time the potential clinical application of previous published data cited above. Translating these results, we conducted a phase I clinical study of vorinostat and niacinamide in relapsed/refractory lymphoma which demonstrated an ORR of 24% (NCT00691210). This proof-of-principle study demonstrates a potential role of combined HDAC inhibition therapy in B-cell lymphomas (8). In addition, it suggests that the cumulative epigenetic derangements of GC-DLBCL may be amenable to targeted therapy through modulation of the acetylation state.

3.

[figure not shown]
**Combined targeting with HDAC and DNMT inhibitors.** Converse to the effects of acetylation, DNA hypermethylation can lead to transcriptional silencing of tumor suppressor genes and resistance to chemotherapy. Unlike HATs, mutations in DNMTs have not been identified in DLBCL, however they have been found to be overexpressed (DNMT1 by 48%) and this has been linked to clinical stage(30). Pre-clinical studies have shown that histone deacetylation and DNA methylation are linked, and cooperate to inactivate a host of tumor suppressor genes (31). *We have demonstrated synergy between HDAC and DNMT inhibitors in T- and B-cell lymphomas(9, 10). The combination of decitabine with panobinostat demonstrated potent*

synergy in vitro, which was validated in a xenograft model of GC-DLBCL where the combination led to marked

[figure not shown]
[figure not shown]
**Figure 6:** Combination of niacinamide with HDAC inhibitors is synergistic in GC-DLBCL

**Figure 7:** Combination of niacinamide with romidepsin leads to acetylation of Bcl6 and p53 in mice and decreased tumor burden

**Figure 8:** Panobinostat is synergistic with decitabine in preclinical models of GC- DLBCL

*tumor growth delay compared to either agent alone (Fig 8).* This combination also led to unique effects on gene expression, where treatment with panobinostat led to an increase in *SMAD1* and *DNMT3A* which may explain the synergistic benefit of DNMT and HDAC inhibition(10). This concept has been recently translated to the clinic in a study of azacitidine in combination with romidepsin for the treatment of patients with relapsed/refractory lymphomas (NCT 01998035)(32) and as a method to re-sensitize DLBCL to chemotherapy (NCT 0243536) (33). These findings underscore that modulating both acetylation and methylation has a path to the clinic for GC-DLCBL.

#### **2.4.2 Phase I Experience and Determination of MTD**

Twenty-six patients were enrolled in the Phase I study and were evaluable for toxicity. Median age was 51 yrs (23-79) and 58% were male. The median number of prior therapies was 6.5 (range 1-18). Histologies included HL (N=12), DLBCL (N=5), follicular lymphoma (N=3), ATLL (N=2), CTCL (N=2), cutaneous ALCL (N=1), T-ALL (N=1). The entry dose in cohort 1 was azacytidine at 100 mg day 1 to 14 with romidepsin 10 mg/m^2 day 8, 15 every 21 days with no DLT detected. There were 2 DLTs in cohort 2 (azacytidine 200mg day 1 to 14 with romidepsin 10 mg/m^2 day 8, 15 every 21 days) consisting of 1 Grade 3 thrombocytopenia and 1 Grade 3 pleural effusion. In cohort 3, 3 additional patients were evaluated using the every 28 days schedule at the same dose level and no thrombocytopenia and/or other DLTs were observed. Dose escalation was continued until 2 DLT were observed in cohort 7 (azacytidine 300mg day 1 to 21 with romidepsin 14mg/m^2 day 8, 15, 22 every 35 days which resulted in 1 Grade 4 thrombocytopenia and 1 Grade 4 neutropenia. This dose level was declared maximum administered dose (MAD). Patients dosed at the maximum tolerated dose (MTD) of azacytidine 300 mg day 1 to 14 and romidepsin 14 mg/m^2 day 8, 15, 22 every 35 days did not experience any toxicities.

The toxicities reported in >10% of patients included: grade 3/4 toxicities represented by febrile neutropenia (19.2%) and thrombocytopenia (19.2%); grade 2 toxicities represented by back pain (7.7%), fatigue (11.5%), nausea (34.6%), vomiting (19.2%), pain (7.7%) and peripheral sensory neuropathy (7.7%) and grade 1 toxicities including fatigue (38.5%), nausea (23%), diarrhea (19.2%), malaise (19.2%), vomiting (19.2%), anorexia (15.4%), pain (15.4%), constipation (11.5%), cough (11.5%), fever (11.5%), general disorders and administration site complains (11.5%), dyspnea (7.7%), hypokalemia (7.7%), insomnia (7.7%), oral mucositis (7.7%) and pruritus (7.7%).

### 3. PATIENT SELECTION

#### 3.1 Inclusion Criteria for Lymphoma

**3.1.1** Phase I: Patients must have histologically confirmed relapsed or refractory non-Hodgkin lymphoma or Hodgkin lymphoma (WHO criteria), with no accepted curative options.

Phase II: Patients with untreated, relapsed or refractory T-cell lymphoma, including patients with central nervous system (CNS) involvement or lymphomatous meningitis are allowed on study.

**Exploratory Cohort:** Patients with histologically confirmed relapsed or refractory Germinal Center (GC)-derived B-Cell Lymphoma (diffuse large B-cell (DLBCL) and follicular lymphoma (FL)) defined by the WHO and Hans criteria with no accepted curative options. (Appendix 5)

**3.1.2.** There is no upper limit for the number of prior therapies. Patients may have relapsed after prior autologous or allogeneic stem cell transplant.

**3.1.3** Evaluable Disease in the Phase I, and measurable disease as defined in Section 11.1 for the Phase II.

**3.1.4** Age  $\geq 18$  years.

**3.1.5** ECOG performance status  $\leq 2$

**3.1.6** Patients must have adequate organ and marrow function as defined below:

- absolute neutrophil count  $\geq 1,000/\text{dL}$
- platelets  $\geq 75,000$  total ( $\geq 50,000$  if bone marrow involvement)
- bilirubin  $\leq 1.5X$  institutional limits
- AST(SGOT)/ALT(SGPT)  $\leq 2.0X$  institutional upper limit of normal
- Serum creatinine within normal institutional limits

OR

- Creatinine clearance  $\geq 50 \text{ mL/min}$  for patients with creatinine levels above institutional normal.

**3.1.7** Negative urine or serum pregnancy test for females of childbearing potential

**3.1.8** All females of childbearing potential must use an effective barrier method of contraception (either an IUDC or double barrier method using condoms or a diaphragm plus spermicide) during the

treatment period and for at least 1 month thereafter. Male subjects should use a barrier method of contraception during the treatment period and for at least 3 months thereafter. Female subjects should avoid the use of estrogen-containing contraceptives, since Romidepsin may reduce the effectiveness of estrogen-containing contraceptives.

**3.1.9** Ability to understand and the willingness to sign a written informed consent document.

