### Study Design:

This is an open label, phase I/IIa, 3 x 3 dose-escalation study with an initial phase I followed by a disease focused phase II.

The primary objective of the phase I is to determine the maximum tolerated dose (MTD) and dose limiting toxicity (DLT) of the combinations of oral 5-azacitidine and romidepsin in patients with lymphoma. The safety and toxicity of this combination will be evaluated throughout the entire study.

If the combination of oral 5-azacitidine and romidepsin is found to be feasible and an MTD is established, the phase II part of the study will be initiated.

Phase II will consist of a 2 stage design of the combination of oral 5-Azacitidine and romidepsin for patients with relapsed or refractory T-cell lymphomas.

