**Primary Objectives**

- Estimate the ORR (complete + partial response) of the combination of oral 5-azacitidine and romidepsin in patients with relapsed/refractory T-cell Lymphoma.

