**Target Population**

**Phase I:** Patients with relapsed or refractory non-Hodgkin lymphoma, Hodgkin lymphoma

**Phase II:** Patients with untreated or relapsed or refractory T-Cell Lymphoma

**Exploratory Cohort:** Patients with relapsed or refractory Germinal Center-Derived B-Cell Lymphoma

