**Inclusion Criteria**

- **Phase I:** Patients must have histologically confirmed relapsed or refractory non-

Hodgkin lymphoma or Hodgkin lymphoma (defined by WHO criteria), with no accepted curative options.

**Phase II:** Patients must have histologically confirmed T-cell lymphoma (as defined by WHO criteria), including central nervous system (CNS) involvement or lymphomatous meningitis.

**Exploratory Cohort:** Patients with histologically confirmed relapsed or refractory Germinal Center (GC)-derived B-Cell Lymphoma (diffuse large B-cell (DLBCL) and follicular lymphoma (FL)) defined by the WHO and Hans criteria with no accepted curative options. (Appendix 5)

- There is no upper limit for the number of prior therapies
- Evaluable Disease in the Phase I, and measurable disease as defined in Section 11.1 in the Phase II.
- Age  $\geq 18$  years.
- ECOG performance status  $\leq 2$
- Patients must have adequate organ and marrow function as defined in Section 3.1.6
- Adequate Contraception
- Ability to understand and the willingness to sign a written informed consent document.

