## Treatment Plan (Phase I)

Patients will be treated with oral 5-azacitidine and romidepsin administered as follows (detailed in Table 2): escalating oral 5-azacitidine from Days 1-14 (Dose cohorts -1 to 5) or Days 1-21 (Dose Cohort 6); and romidepsin administered intravenously on Days 8, 15 (Dose cohorts 1-4) of a 28 day cycle and Day 22 (Dose Cohorts 5 and 6) of a 35 day cycle. Cohorts of 3 patients will be enrolled sequentially as outlined in the dose escalation scheme

(Table 2). Once the MTD is reached the Phase II part of the protocol will be initiated in patients with T-Cell Lymphoma (Figure 2).

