## A. Schema Phase II and Exploratory Cohort

- Oral 5-azacitidine and romidepsin administered at the MTD of the combination to patients with T-Cell Lymphoma: oral 5-azacytidine at 300 mg (flat dose) Days 1-14 and romidepsin 14 mg/m^2 on Days 8, 15 and 22 on a 35 day cycle.
- For Exploratory Cohort Only: Lymph node biopsy for determination of gene expression profile

### CYCLE 1

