### **1.4 Phase II Primary Objectives**

- Estimate the ORR (complete + partial response) of the combination of oral 5-azacitidine and romidepsin in patients with relapsed/refractory T-Cell Lymphoma.

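### The Phase II objective and two-stage design are stated for relapsed/refractory T-cell lymphoma, but eligibility admits untreated patients and the counting rules would include them

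*Combined protocol and SAP*

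**What the plan says.** The combined protocol and SAP describes the Phase II population in several ways.

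- **Relapsed or refractory.** The synopsis (Study Design) describes a two-stage design of the "combination of oral 5-Azacitidine and romidepsin for patients with relapsed or refractory T-cell lymphomas". The primary objective, in the synopsis and again in section 1.4, is the ORR of "oral 5-azacitidine and romidepsin in patients with relapsed/refractory T-Cell Lymphoma".
- **Untreated patients admitted.** The synopsis (Target Population) has "Patients with untreated or relapsed or refractory T-Cell Lymphoma". Section 3.1.1 has "Phase II: Patients with untreated, relapsed or refractory T-cell lymphoma".
- **Line of therapy not given.** The synopsis inclusion criteria ask only for histological confirmation of T-cell lymphoma. The Phase II schema has treatment "administered at the MTD of the combination to patients with T-Cell Lymphoma".
- **Recurrent or refractory disease required.** Section 9.2.1 makes a biopsy confirming this a condition of participation. That section is headed as optional biopsies, and section 4.2 asks for a biopsy in the relapsed setting only where applicable.
- **PTCL.** Section 13.1 (Phase II) names peripheral T-cell lymphoma and says nothing about prior treatment.

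Section 13.2 sets one rule for 9 + 15 = 24 patients: stop at 2 or fewer responses among the first 9, and drop the combination at 9 or fewer among 24. The null is an ORR of 25% or less and the alternative 50% or more. The stage 1 sentence refers to a stratum, but the plan defines none. Section 11.1.1 treats a patient as evaluable for response after one day of therapy and a disease re-evaluation. Section 11.2.5 bases ORR on each patient's best response, and section 13.3 takes best response by 4 cycles. None of these draws a line by prior treatment.

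**The concern.** In a single-arm trial the go/no-go decision is a count of responders against a fixed null, so its meaning depends on who is counted and on the population to which the null belongs. Here the objective names a subset of those whom eligibility admits, while the counting rules make no such distinction. A trial run exactly as section 13.2 is written could therefore reach 10 of 24 partly on untreated responders and be reported as a result for relapsed/refractory disease.

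If the team instead leaves untreated patients out to match the objective, fewer than 24 are counted and the printed error rates no longer apply. If the choice is left until responses are known, one untreated responder at a boundary could decide continuation or success.

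**Working it through.** **Inputs from the plan (section 13.2).** p0 = 0.25, p1 = 0.50, n1 = 9, n = 24; continue at X1 ≥ 3; success at X1 + X2 ≥ 10. Printed: alpha 0.049, power 80%, early stopping 0.60, expected N 15.

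**Step 1: reproduce the design.** With X1 ~ Bin(9, p) and X2 ~ Bin(15, p):

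- Early stopping = P(X1 ≤ 2 | 0.25) = 0.0751 + 0.2253 + 0.3003 = 0.6007.
- Expected N = 9 + (1 − 0.6007) × 15 = 14.99.
- P(go | p) = Σ over x = 3 to 9 of P(X1 = x) · P(X2 ≥ 10 − x), which is 0.0485 at p = 0.25 and 0.8055 at p = 0.50.

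These agree with the plan, apart from a third-decimal difference in alpha. A full search for the optimal two-stage design at alpha ≤ 0.05 and power ≥ 0.80 returns the same 2/9 and 9/24. The design arithmetic is sound.

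**Step 2: untreated patients counted.** Assumptions, because the documents give neither figure: u1 untreated patients in stage 1 and u2 in stage 2, each responding with probability q. Relapsed/refractory patients respond at the null 0.25. Then X1 = Bin(u1, q) + Bin(9 − u1, 0.25), X2 = Bin(u2, q) + Bin(15 − u2, 0.25), and false-go = P(X1 ≥ 3 and X1 + X2 ≥ 10).

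| Untreated of 24 (stage 1 + stage 2) | q = 0.25 | q = 0.40 | q = 0.50 |
|---|---|---|---|
| 0 | 0.0485 | 0.0485 | 0.0485 |
| 1 (0 + 1) | 0.0485 | 0.0552 | 0.0598 |
| 1 (1 + 0) | 0.0485 | 0.0570 | 0.0627 |
| 3 (1 + 2) | 0.0485 | 0.0733 | 0.0929 |
| 6 (2 + 4) | 0.0485 | 0.1063 | 0.1616 |

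Below the null the error falls: 6 untreated (2 + 4) at q = 0.20 gives 0.0351. For 6 untreated at q = 0.40, the split between stages moves false-go only from 0.098 (none in stage 1) to 0.116 (all six). Early stopping moves more: 0.60 with none in stage 1, 0.51 with two, 0.33 with all six.

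**Step 3: untreated patients enrolled within the 24 but not counted, cut-offs unchanged.** Power at p = 0.50:

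- 3 untreated, 8 + 13 = 21 counted: 0.632.
- 6 untreated, 7 + 11 = 18 counted: 0.387.

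The design value is 0.805.

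**Step 4: the mixture as the intended population.** The true rate is then the mixture's own. With 6 of 24 at 40%, it is (6 × 0.40 + 18 × 0.25)/24 = 6.9/24 = 28.75%, above the null, so a go decision would not be an error. A go decision is a type I error only where the mixture's ORR is 25% or less. The step 2 figures do not apply on this reading.

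**The case against.** The strongest reply is that the plan does say who counts. Section 13.2 speaks of patients treated in stage 1 and a total studied of 24, the same 24 that the synopsis says Phase II will accrue, and sections 11.1.1 and 11.2.5 exclude nobody by prior treatment. This stands: a reader might infer that the plan is silent on counting, and that goes too far. It does not remove the problem, because the population so counted is not the one in the objective.

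Second, the target population and section 3.1.1 agree with each other, so untreated patients look deliberately admitted. That may be so. If it is, the objective and the design sentence are misworded and the 25% null still lacks a stated population.

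Third, section 9.2.1 read literally gives no untreated patients and no effect on the error rate. Its place under optional biopsies and the conditional wording in section 4.2 stop it from settling the matter against an explicit inclusion criterion.

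Fourth, the size rests on assumptions. This also stands. A reader might infer from the table that the printed 0.049 is breached. The documents do not support that: they give no untreated count and no untreated response rate, and the error can stay the same or fall.

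**Conclusion.** The contradiction is in the current text and needs no assumption: the objective and two-stage design are for relapsed/refractory disease, eligibility is wider, one section demands biopsy proof of recurrent or refractory disease, and section 13.1 names PTCL. If any untreated patient enrols within the 24, no reading keeps both the objective and the printed operating characteristics assured.

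The numbers show sensitivity only. With relapsed/refractory ORR at 25% and an assumed untreated ORR of 40% to 50%, counting untreated patients moves false-go from 4.85% to between 5.5% and 6.3% with one, and to 16.2% at most with six (2 in stage 1). Leaving three or six uncounted within the 24 costs power instead.

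The reference to a stratum is a related drafting fault. It cannot be taken as a plan to stratify by prior treatment, because no stratum is defined. Since who counts defines the only efficacy decision in Phase II, this should be settled before responses are reviewed.

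**What to change.** Before responses are reviewed, reconcile the synopsis (Study Design, Phase II Primary Objectives, Target Population, Inclusion Criteria) and sections 1.4, 3.1.1, 9.2.1, 13.1 and 13.2 so that one Phase II population is named, including whether it is PTCL or T-cell lymphoma. Define or delete the stratum in 13.2. The choice of population is the sponsor's.

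**(A) If the objective stays relapsed/refractory.** Either make eligibility match it, or add to 13.2 and 13.3: *Only patients with relapsed or refractory disease count toward the first 9, the 24 and the primary ORR; untreated patients are additional to the 24 and are summarised separately.* If fewer than 24 will be counted, recompute both boundaries and restate alpha and power.

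**(B) If untreated patients are meant to be tested.** Reword the objective and the design sentence, say in 13.2 that all enrolled Phase II patients count, justify the 25% null for that mixture, and report ORR separately by prior-treatment status.

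The cost is amendment wording and one extra table. Under (A), accrual may be slower, or a few patients are enrolled beyond the 24.
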